#### 3.1.7.4 Renal Function:

- A serum creatinine based on age/gender as follows:

Age	Maximum Serum Creatinine (mg/dL)	
	Male	Female
12 to < 13 years	1.2	1.2
13 to < 16 years	1.5	1.4
$\geq 16$ years	1.7	1.4

OR

- Creatinine clearance  $\geq 70$  mL/min/1.73 m^2 for participants with creatinine levels above institutional normal.

#### 3.1.7.5 Adequate Cardiac Function: QTc $\leq 480$ msec on ECG

#### 3.1.7.6 Adequate GI Function: Diarrhea < grade 2 by CTCAE version 5

#### 3.1.7.7 Adequate Metabolic Function: Fasting glucose $\leq 160$ mg/dL (or $\leq 8.9$ mmol/L) without the use of antihyperglycemic agents. If random glucose $\leq 160$ mg/dL (or $\leq 8.9$ mmol/L), fasting value does not need to be obtained.

### 3.1.8 Additional Agent-Specific Requirements

#### 3.1.8.1 Patients must be able to swallow pills.

#### 3.1.7.3 For patients with CNS metastatic disease, any baseline neurologic deficits (including seizure) must be stable for at least one week prior to study enrollment.

#### 3.1.9 Ability to understand and/or the willingness of the patient (or parent or legally authorized representative, if minor) to provide informed consent, using an institutionally approved informed consent procedure.

### 3.2 Exclusion Criteria

3.2.1 Patients must not be receiving any of the following concomitant medications:

3.2.1.1 Pharmacologic doses of systemic corticosteroids unless for CNS metastatic disease. For patients with CNS metastatic disease receiving corticosteroids, they should be on a stable or decreasing dose over the 7 days prior to registration and meet criteria in Section 3.1.6.7.

For all patients, receipt of systemic physiologic replacement steroids, topical and/or inhaled corticosteroids is acceptable.

3.2.1.2 Patients receiving medications that are strong inhibitors or inducers of CYP3A4 within 7 days of enrollment (refer to Appendix B, **Table 10** for prohibited medications)

3.2.1.3 Patients receiving medications that cause significant QTc prolongation as outlined in **Table 12** of Appendix B.

3.2.2 Patients who have had tumor molecular testing with sequencing of the RB1 gene and were found to have RB1 mutation or loss will be excluded.

3.2.3 Patients with a history of pneumonitis will be excluded.

3.2.4 Pregnant participants will not be entered on this study given that the effects of palbociclib and ganitumab on the developing human fetus are unknown.

3.2.5 Because there is an unknown but potential risk for adverse events in nursing infants secondary to treatment of the mother with palbociclib and ganitumab, breastfeeding mothers are not eligible.

3.2.6 Participants of child-bearing or child-fathering potential must agree to use adequate contraception (hormonal birth control; intrauterine device; double barrier method; or total abstinence) throughout their participation, including up until 30 days after last dose of palbociclib or ganitumab, whichever was administered last.

3.2.7 History of allergic reactions attributed to compounds of similar chemical or biologic composition to palbociclib or ganitumab.

3.2.8 Uncontrolled intercurrent illness including, but not limited to, ongoing or active infection, symptomatic congestive heart failure, unstable angina pectoris, cardiac arrhythmia, or psychiatric illness/social situations that would limit compliance with study requirements.

3.2.9 Participants with a personal history of any of the following: syncope due to an intrinsic cardiac etiology (note that syncope due to vasovagal episodes or dehydration/orthostasis would NOT exclude a participant), pathologic ventricular arrhythmias (including, but not

limited to, ventricular tachycardia and ventricular fibrillation), or sudden cardiac arrest.

3.2.10 Patients with known HIV, hepatitis B, and/or hepatitis C (testing not required as part of screening).

3.2.11 Patients with a known history of type 1 or type 2 diabetes mellitus.

3.2.12 Patients with gastrointestinal disease or disorder that could interfere with absorption of palbociclib, such as bowel obstruction or inflammatory bowel disease.

3.2.13 Patients < 40 kg will be excluded given use of palbociclib at non-weight / non-BSA based flat dosing.

3.2.14 Patients with prior invasive malignancies within 5 years are excluded, with the exception of curatively-treated basal cell or squamous cell carcinoma of the skin or carcinoma *in situ* of the cervix.

### **3.3 Inclusion of Children and Minorities**

Both male and female children and young adults of all races and ethnic groups are eligible for this trial.

## **4 REGISTRATION PROCEDURES**

### **4.1 General Guidelines for All Sites**

DF/HCC Standard Operating Procedure for Human Subject Research Titled *Subject Protocol Registration* (Policy #: REGIST-101) must be followed.

Eligible participants will be registered in the Clinical Trials Management System (CTMS) OnCore. Registrations must occur prior to the initiation of protocol therapy. Any participant not registered to the protocol before protocol therapy begins will be considered ineligible and registration will be denied.

An investigator will confirm eligibility criteria and will complete and sign the protocol-specific eligibility checklist.

Following registration, participants may begin protocol therapy and should begin protocol therapy within 5 calendar days. Issues that would cause treatment delays should be discussed with the Overall Principal Investigator (PI). If a participant does not receive protocol therapy following registration, the participant's registration on the study must be canceled. Registration cancellations must be made in OnCore as soon as possible.

## **5 TREATMENT PLAN**

[figure not shown]
## 5.1 Treatment Regimen

### 5.1.1 Overview of Treatment Regimen

Once enrolled, patients will begin therapy in 28-day cycles with palbociclib orally once daily on days 1-21 according to the below Cohort dosing, and ganitumab 18 mg/kg on days 1 and 15 as shown in **Figure 4**. Disease will be evaluated at baseline, after cycle 2, 4, 6, 8, 10 and 12.

Palbociclib dosing:

- Cohort A – Palbociclib 100 mg orally daily on days 1-21
- Cohort B – Palbociclib 125 mg orally daily on days 1-21

**Figure 4:** Treatment overview

Patients may begin therapy on any day of the week as an inpatient or as appropriate for the outpatient clinic schedule. A window of +/- 3 days around Day 1 cycle start dates and +/- 1 day around Day 15 ganitumab administration is allowable for logistical reasons.

Appropriate dose modifications are described in Section 6. Reported adverse events and potential risks are described in Section 7. No investigational or commercial agents or therapies other than those described below may be administered with the intent to treat the participant's malignancy.

In the absence of criteria for removal from protocol therapy (see Section 5.6), participants may continue to receive the study regimen for up to 12 cycles (approximately 12 months of therapy).

## 5.2 Pre-Treatment Criteria

### 5.2.1 Cycle 1, Day 1

If screening laboratory and diagnostic studies for registration were obtained  $> 5$  days prior to Cycle 1, Day 1, then **the following studies must be repeated within 5 days of Cycle 1, Day 1 and prior to the Cycle 1, Day 1 palbociclib and ganitumab dose: CBC; creatinine or creatinine clearance; bilirubin; ALT; serum albumin; fasting or random glucose** (see Section 3.1.7.7).

If any of these repeat laboratory studies do not meet organ function requirements in Section 3.1.7, then the patient must not receive protocol therapy. In this case, laboratory studies may be repeated again within 5 days. If these laboratory studies now meet eligibility requirements, the patient may proceed with protocol therapy, otherwise the patient will be removed from study.

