### **3 PARTICIPANT SELECTION**

Prior to approaching a potential participant, treating investigators should reserve a treatment slot by contacting the Study Coordinator. Upon reserving a treatment slot, an investigator may begin the informed consent process for that participant. Once informed consent has been obtained, the investigator may begin screening studies to confirm eligibility. Once all eligibility criteria have been satisfied, the investigator may enroll the participant according to Section 4.0.

Baseline laboratory tests and ECG must be completed within 14 days prior to the date of enrollment. Laboratory tests used to meet eligibility requirements may be completed within 14 days prior to date of enrollment, but select tests must be repeated within 5 days prior to dosing on Cycle 1, Day 1 if obtained > 5 days prior to Cycle 1, Day 1 as described in Section 5.2. If repeat laboratory studies no longer meet eligibility requirements, the patient must not receive protocol therapy. In this case, required studies may be repeated again within 5 days. If these studies now meet eligibility requirements, the patient may proceed with protocol therapy, otherwise the patient will be removed from study and replaced.

Baseline disease assessments (such as MRIs, CT scans, bone marrow biopsies, and nuclear medicine studies) must be performed within 28 days prior to the date of enrollment.

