3.1.7 Participants must have normal organ function as defined below.

3.1.7.1 Hematologic Requirements for Subjects without Known Bone Marrow Involvement by Disease:

- Absolute neutrophil count       $>1000 / \mu\text{L}$
- Hemoglobin       $\geq 8 \text{ g/dL}$  (transfusion allowed)
- Platelets       $\geq 100,000 / \mu\text{L}$  and transfusion independent, defined as not receiving a platelet transfusion for at least 7 days prior to CBC documenting eligibility.

3.1.7.2 Hematologic Requirements for Subjects with Bone Marrow Involvement by Disease as Demonstrated on Clinically-Indicated Bone Marrow Biopsy:

- Absolute neutrophil count       $>750 / \mu\text{L}$
- Hemoglobin       $\geq 8 \text{ g/dL}$  (transfusion allowed)
- Platelets       $\geq 50,000 / \mu\text{L}$  and transfusion independent, defined as not receiving a platelet transfusion for at least 7 days prior to CBC documenting eligibility.

- Not known to be refractory to platelet or red cell transfusions.

3.1.7.3 Hepatic Function:

- Total bilirubin       $\leq 1.5 \times$  upper limit of normal for age  
Patients with Gilbert's syndrome with a total bilirubin  $< 2 \times$  upper limit of normal for age and

• ALT (SGPT)	a direct bilirubin within normal limits are permitted. $\leq 135$ U/L For the purpose of this study, the ULN for ALT is 45 U/L
• AST	$\leq 90$ U/L For the purpose of this study, the ULN for AST is 30 U/L
• Serum albumin	$\geq 2$ g/dL

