### 5.2.2 Subsequent Cycles

Prior to the start of each subsequent cycle of therapy, patients without bone marrow involvement must meet all of the following criteria:

- No clinical or radiographic evidence of disease progression;
- Meet hematologic, renal, hepatic, and metabolic organ function requirements listed in Section 3.1.7, with the following exception:
  - ANC  $\geq 750/\mu\text{L}$
  - Platelets  $\geq 75,000/\mu\text{L}$  and transfusion independent, defined as not receiving a platelet transfusion for at least 5 days prior to CBC
- All other adverse events at baseline or  $\leq$  grade 2, whichever is lower.

Prior to the start of each subsequent cycle of therapy, patients who enrolled with bone marrow involvement as demonstrated on a clinically indicated bone marrow must meet all of the following criteria:

- No clinical or radiographic evidence of disease progression;
- Meet hematologic, renal, hepatic, and metabolic organ function requirements listed in Section 3.1.7, with the following exception:
  - ANC  $\geq 500/\mu\text{L}$
  - Platelets  $\geq 50,000/\mu\text{L}$  and transfusion independent, defined as not receiving a platelet transfusion for at least 5 days prior to CBC
- All other adverse events at baseline or  $\leq$  grade 2, whichever is lower.

Laboratory studies to meet these requirements may be obtained within 3 days of Day 1 of each cycle.

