### OBTAINT OTHER STUDIES AS NEEDED FOR GOOD PATIENT CARE.

1. Laboratory studies obtained in screening do not need to be repeated on Cycle 1, Day 1, UNLESS obtained  $> 5$  days prior to Cycle 1 Day 1. In that event repeat the following: CBC; creatinine or creatinine clearance; bilirubin; ALT; albumin; fasting glucose or random glucose.
2. End of therapy visit and observations should be performed within 7 days of decision to permanently discontinue palbociclib and ganitumab ( $\pm 7$  days).
3. All participants will have a follow-up visit approximately 30-days following their last dose of study therapy. days or until all toxicity related to the study drug has resolved, whichever is longer. For participants who are unable to return to the study center, observations may be performed at referring center.
4. Vital signs include temperature, heart rate, blood pressure, respiratory rate, and oxygen saturation.

5. Required for verification of eligibility. Creatinine clearance may be required at screening if creatinine does not meet criteria in Section 3.1.6.3.
6. More frequent CBCs and chemistries may be needed as part of good patient care, particularly if adverse events noted during more frequent lab screenings during Cycles 1 and 2.
7. Obtain for females 12 years of age and older or post-pubertal.
8. Studies obtained as part of disease evaluation will depend upon underlying sites of disease and initial imaging modalities. Studies may include anatomic imaging, nuclear imaging, bone marrow biopsies. Baseline disease status tests must be performed  $\leq$  28 days prior to study registration and subsequent to any intervening therapy.
9. Perform disease re-staging during Week 3 or 4 of Cycles 2, 4, 6, 8, 10 and 12. Confirmatory scans will also be obtained 4 weeks following initial documentation of an objective response (partial response or better).
10. Once a participant is off protocol therapy, they will be followed for survival until one year after the last dose of protocol therapy is given to the last enrolled patient. Participants will undergo disease surveillance at the discretion of their local treating physician following completion of study therapy.

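### The repeat-test list before the first dose omits AST and the pregnancy test, so both results can be about 19 days old when the listed tests are at most 5 days old

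*Combined protocol and SAP*

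**What the plan says.** Section 3 sets the screening window: "Baseline laboratory tests and ECG must be completed within 14 days prior to the date of enrollment". Section 4.1 says that a registered participant "should begin protocol therapy within 5 calendar days", and that expected delays are to be discussed with the overall principal investigator. Section 3 and the introduction to Section 10 add that selected tests are repeated if they are more than 5 days old at Cycle 1 Day 1.

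The selection appears in two places, and they agree. Section 5.2.1 lists "CBC; creatinine or creatinine clearance; bilirubin; ALT; serum albumin; fasting or random glucose". Calendar footnote 1 says: "In that event repeat the following: CBC; creatinine or creatinine clearance; bilirubin; ALT; albumin; fasting glucose or random glucose". Section 5.2.1 withholds treatment only if one of those repeated tests fails Section 3.1.7.

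On AST, Section 3.1.7.3 sets an entry limit of 90 U/L and fixes the reference value: "For the purpose of this study, the ULN for AST is 30 U/L". For later cycles Section 5.2.2 says: "Meet hematologic, renal, hepatic, and metabolic organ function requirements listed in Section 3.1.7, with the following exception". The exceptions that follow concern ANC and platelets only, and the labs must be within 3 days of Day 1.

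On pregnancy, Section 3.2.4 states: "Pregnant participants will not be entered on this study given that the effects of palbociclib and ganitumab on the developing human fetus are unknown". The calendar row for the pregnancy test is marked at screening, blank for Cycle 1, and due at the start of Cycle 2 and each later cycle. Calendar footnote 5, which marks tests needed to verify eligibility, is attached to both the AST/ALT row and the pregnancy-test row.

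**The concern.** Section 5.2.1 exists to confirm, just before first exposure, that a patient still meets the organ-function criteria when the screening labs have aged. AST is one of those criteria but is not on the list, although ALT, bilirubin and albumin from the same subsection are. No reason is given for keeping ALT and leaving out AST. The plan then applies the AST limit before every later cycle on a tighter window, so the first dose is the only cycle start at which a stale AST is acceptable.

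The pregnancy test has a similar gap in the calendar: it is scheduled at screening and at every cycle start except the first. The plan itself says that fetal effects of the two drugs are unknown. At stake are dosing a patient who no longer meets an entry criterion, and a first fetal exposure that Section 3.2.4 is meant to prevent.

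**Working it through.** The plan states no figure for the age of these results, so there is none to reproduce. The check is a comparison of the passages and one sum.

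**Side by side**

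| Test | Used for eligibility | Cycle 1 Day 1 repeat (5.2.1 and footnote 1) | Later cycles |
|---|---|---|---|
| ALT, bilirubin, albumin | 3.1.7.3 | Listed | 5.2.2, labs within 3 days |
| AST | 3.1.7.3 (at most 90 U/L = 3 × 30) | Not listed | 5.2.2, labs within 3 days |
| Pregnancy test | 3.2.4 and calendar footnote 5 | Not listed; Cycle 1 cell blank | Calendar only, start of cycle |

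**Inputs**

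- Screening window before enrollment: 14 days (Sections 3 and 10).
- Registration to first dose: 5 calendar days, worded as a recommendation (Section 4.1).
- Enrollment is taken to be registration, because Section 3 enrolls participants through Section 4.
- Oldest result allowed for a listed test at Cycle 1 Day 1: 5 days (Section 5.2.1).
- Oldest AST allowed at a later cycle start: 3 days (Section 5.2.2).

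**Age of the result at first dose**

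Maximum age = screening window + days from registration to first dose.

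- AST and pregnancy test: 14 + 5 = 19 days.
- Listed tests: 5 days, so the gap is 19 − 5 = 14 days.
- AST at a later cycle start: 3 days, so the gap is 19 − 3 = 16 days.
- If the 3-day allowance around Day 1 of a cycle (Section 5.1.1) is taken to cover Cycle 1: 19 + 3 = 22 days.
- With both tests on the repeat list: 5 days.

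**Who passes the check as written**

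For AST, the patient must have AST above 90 U/L while ALT is still at or below 135 U/L and bilirubin and albumin still meet Section 3.1.7.3. If any of those three has also moved out of range, the existing list stops treatment. For pregnancy, it is a patient who tested negative at screening and has become pregnant since.

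**Does another passage close the gap?**

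The calendar shows the liver panel, including AST, as weekly in Cycle 1. Footnote 1, attached to that column, releases Day 1 from repeat testing unless screening is more than 5 days old, and then names only the six tests. A weekly draw also does not have to be resulted before the dose. No other section adds AST or a pregnancy test before the first dose.

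**The case against.** The best defence is that the subset was chosen. The plan speaks of selected tests, its two lists agree, and no two passages contradict each other outright. That is so: this is a gap against the plan's own entry criteria and later checks, not a conflict between the lists. But nothing explains why AST was left out, and Section 5.2.2 applies the same limit at every later cycle.

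It is also fair that most of the hepatic check is intact, so the AST route is narrow. For pregnancy, the screening test, the contraception requirement in Section 3.2.6 and removal from therapy under Section 5.6 lower the risk. They do not remove it, and the same safeguards apply in later cycles, where the calendar still calls for a test.

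A reader might infer three stronger things that the documents do not support:

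- *That both items are gated before every later cycle.* Only AST is in the Section 5.2.2 criteria. The pregnancy test comes from the calendar, under a general 3-day window either side, and is not an explicit condition for dosing.
- *That results could be 24 days old*, by adding the further 5-day repeat allowance (19 + 5). This needs a listed test to fail first, and Section 5.2.1 does not say that the allowance runs after the full 5-day start window.
- *That a raised pre-treatment AST could be counted as a DLT and push a cohort toward its three-DLT pause.* An AST just over 90 U/L is not a DLT in itself. Section 5.4.1 requires attribution to study drug and also a higher grade, an accompanying bilirubin rise, or persistent intolerable Grade 2 toxicity that requires interruption. ALT, bilirubin and albumin are re-checked, and the screening AST is on file. The chain is speculative.

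**Conclusion.** The point holds as a bounded safety gap that should be closed. Followed literally, the plan allows a first dose on AST and pregnancy results nominally up to 19 days old, against 5 days for the listed tests. The 19 days assumes that enrollment and registration are the same event and that the recommended 5-day start is kept. It is not a ceiling: the start may slip after discussion with the principal investigator, and no upper limit is given. The documents give no basis for estimating how many patients would be affected, and for AST the number is likely to be small. The point does not bear on the primary response analysis or on the operating characteristics of the toxicity rule.

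**What to change.** Reconcile Section 5.2.1 and calendar footnote 1 with Sections 3.1.7.3, 3.2.4 and 5.2.2 and with the calendar rows. The Cycle 1 Day 1 repeat list would then cover AST, and the Cycle 1 cell for the pregnancy test would match Cycle 2 and later for the patients described in calendar footnote 7. This uses only tests and limits already in the plan. If the shorter list is intended, the plan should say so and give the reason.

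The cost is a line of text in Section 5.2.1 and matching edits in the calendar. AST is already in the same calendar liver panel as ALT. The only added procedure is one serum or urine pregnancy test for some patients.

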### 5.2.2 Subsequent Cycles

Prior to the start of each subsequent cycle of therapy, patients without bone marrow involvement must meet all of the following criteria:

- No clinical or radiographic evidence of disease progression;
- Meet hematologic, renal, hepatic, and metabolic organ function requirements listed in Section 3.1.7, with the following exception:
  - ANC  $\geq 750/\mu\text{L}$
  - Platelets  $\geq 75,000/\mu\text{L}$  and transfusion independent, defined as not receiving a platelet transfusion for at least 5 days prior to CBC
- All other adverse events at baseline or  $\leq$  grade 2, whichever is lower.

Prior to the start of each subsequent cycle of therapy, patients who enrolled with bone marrow involvement as demonstrated on a clinically indicated bone marrow must meet all of the following criteria:

- No clinical or radiographic evidence of disease progression;
- Meet hematologic, renal, hepatic, and metabolic organ function requirements listed in Section 3.1.7, with the following exception:
  - ANC  $\geq 500/\mu\text{L}$
  - Platelets  $\geq 50,000/\mu\text{L}$  and transfusion independent, defined as not receiving a platelet transfusion for at least 5 days prior to CBC
- All other adverse events at baseline or  $\leq$  grade 2, whichever is lower.

Laboratory studies to meet these requirements may be obtained within 3 days of Day 1 of each cycle.

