### 5.3.2 Ganitumab

Ganitumab is administered via IV on days 1 and 15 of each cycle.

Ganitumab will be administered at a dose of 18 mg/kg.

Ganitumab should be administered as follows:

- The infusion line should be thoroughly flushed with saline before and after administration of ganitumab to avoid mixing with other drug products or IV solutions.
- The first dose should be administered over 60 minutes without premedication. If well tolerated over 60 minutes, subsequent infusions may be administered over 30 minutes, at the investigator's discretion. Infusion times can be extended to a maximum of 120 minutes for subjects unable to tolerate the 60-minute infusion.
- Doses over 2100 mg should be infused over 120 minutes. If well tolerated over 120 minutes, subsequent infusions may be administered over 60 minutes at the investigator's discretion.
- The dose of ganitumab is to be based upon the participant's weight in kg obtained within 7 days of the start of each cycle. There is no adjustment for obesity.

See section 8.1.2.5 for ganitumab preparation.

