#### 6.4.2 Management of Hyperglycemia

For patients who develop hyperglycemia (based on random, non-fasting glucose levels), discontinue use of corticosteroids before modifying ganitumab dose. If hyperglycemia occurs without use of corticosteroids, ganitumab therapy modifications should be as follows:

Hyperglycemia Grade (per CTCAE, under Hyperglycemia )	Action
Grade 1	Continue ganitumab.
Grade 2	Continue ganitumab. Consider consultation with Pediatric Endocrinologist.
Grade 3 or Urine glucose > 0.1 g/dL	
 
Initiate insulin therapy or oral diabetic agent* as indicated.
 
Hold ganitumab until resolves to <math>\leq</math> Grade 2 without glycosuria.
 
Resume ganitumab at same dose IF patient is asymptomatic, AND serum glucose is consistently <math><</math> 250 mg/dL (<math>\leq</math> Grade 2) without glycosuria AND resolution to <math>\leq</math> Grade 2 has occurred within 2 weeks of interruption. The patient may continue to receive concomitant insulin or an oral diabetic agent for the management of hyperglycemia while receiving ganitumab.
 
If Grade 3 hyperglycemia recurs despite a stable dose of insulin or oral diabetic agent OR if resolution to consistent levels <math>\leq</math> Grade 2 requires more than 2 weeks of interruption, subsequent doses should be administered with a reduced dose of 12 mg/kg/dose.
 

Grade 4	
 
Initiate insulin therapy as indicated.
 
If associated with diabetic ketoacidosis or hyperosmolar nonketotic syndrome, discontinue ganitumab permanently. Otherwise, use the following instructions.
 
Hold ganitumab until resolves to <math>\leq</math> Grade 2.
 

	
 
Resume ganitumab with a reduced dose of 12 mg/kg/dose IF patient is asymptomatic, AND serum glucose is consistently <math>< 250</math> mg/dL (<math>\leq</math> Grade 2) without glycosuria AND resolution to <math>\leq</math> Grade 2 has occurred within 2 weeks of interruption. The patient may continue to receive concomitant insulin or an oral diabetic agent for the management of hyperglycemia while receiving ganitumab.
 
If resolution to consistent levels <math>\leq</math> Grade 2 requires more than 2 weeks of interruption OR if Grade 4 toxicity recurs after re-challenge with 12 mg/kg, then discontinue ganitumab permanently.
 

--	---

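### Section 5.2.2 blocks the next cycle for hyperglycemia that Section 6.4.2 lets patients be treated through, and its adverse-event cap bars a patient with a new grade 1 event

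*Combined protocol and SAP*

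**What the plan says.** Section 5.2.2 sets the conditions for starting every cycle after the first, in two lists. One opens "patients without bone marrow involvement must meet all of the following criteria"; the other is for patients who enrolled with marrow disease. Each contains the line "Meet hematologic, renal, hepatic, and metabolic organ function requirements listed in Section 3.1.7, with the following exception", and each then relaxes only the neutrophil and platelet limits. The last bullet of each holds every other adverse event to baseline or "grade 2, whichever is lower".

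The metabolic requirement brought in this way is 3.1.7.7: fasting glucose of 160 mg/dL or less "without the use of antihyperglycemic agents". A random value of 160 mg/dL or less also satisfies it.

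Section 6.4.2 manages hyperglycemia on treatment and works from random glucose. Ganitumab continues at grade 1, and the grade 2 row reads "Continue ganitumab. Consider consultation with Pediatric Endocrinologist". After grade 3, and after grade 4 without ketoacidosis or hyperosmolar syndrome, ganitumab resumes once glucose is consistently below 250 mg/dL and the other stated conditions are met. For both grades the table adds: "The patient may continue to receive concomitant insulin or an oral diabetic agent for the management of hyperglycemia while receiving ganitumab". A further rule begins "If Grade 3 hyperglycemia recurs despite a stable dose of insulin or oral diabetic agent".

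Section 6.1, on restart after a DLT, asks for recovery to grade 1 or to baseline, and takes the higher of the two.

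**The concern.** The two sections give opposite answers for the same patient. Section 5.3.2 says "Ganitumab is administered via IV on days 1 and 15 of each cycle". A patient on insulin could thus receive the Day 15 infusion under 6.4.2 and be refused Day 1 of the next cycle under 5.2.2. While the drug is still needed, the permission in 6.4.2 covers at most one infusion (none if onset is after Day 15), out of 12 × 2 = 24 in a full course. The rule in 6.4.2 for recurrence on a stable dose of insulin or oral agent presupposes repeated dosing that 5.2.2 prevents.

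The adverse-event cap has a wider reach. Read literally, new grade 1 fatigue or diarrhea in a patient with none at baseline stops the next cycle. At stake are treatment that Section 6 permits and uniform conduct across sites, since a site must either breach 5.2.2 or withhold the cycle. Section 2.6 makes maximizing exposure to the combination a priority.

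**Working it through.** No stated sample size, power or error rate depends on this point, so the check sets the rules side by side.

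**Glucose.** Section 5.2.2 with 3.1.7.7 allows the cycle if fasting glucose is ≤160 mg/dL and no antihyperglycemic drug is in use. Section 6.4.2 allows ganitumab if hyperglycemia is grade 1-2 or, after grade 3-4, if glucose is consistently <250 mg/dL and its other conditions hold, with or without a drug.

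| Glucose (mg/dL) | Insulin or oral agent | Cycle start, 5.2.2 | Ganitumab, 6.4.2 |
|---|---|---|---|
| 140, 160 | no | yes | yes |
| 161, 200, 249 | no | no | yes |
| 140 to 249 | yes | no | yes |

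The table enters one value in both rules, although 3.1.7.7 is decided on fasting glucose and 6.4.2 on random glucose. The third row does not depend on this, because drug use alone fails 3.1.7.7. The second row holds for fasting values above 160 mg/dL in a patient whose hyperglycemia is still grade 1-2 under 6.4.2. An untreated patient with random glucose above 160 but fasting glucose of 160 mg/dL or less passes both rules.

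**Adverse-event cap.** With baseline grade b, 5.2.2 as written is min(b, 2); the 6.1 restart rule is max(b, 1); replacing *lower* by *higher* in 5.2.2 gives max(b, 2).

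| Baseline grade | 5.2.2 as written | 6.1 rule | *Higher*, grade 2 kept |
|---|---|---|---|
| 0 | 0 | 1 | 2 |
| 1 | 1 | 1 | 2 |
| 2 | 2 | 2 | 2 |
| 3 | 2 | 3 | 3 |

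As written, the grade 2 limit changes nothing for baseline grades 0 to 2 and acts only from grade 3. At baseline 0 the routine cycle start is stricter than restart after a DLT (0 against 1). It is also stricter than entry: 3.1.7.6 admits a patient with grade 1 diarrhea, and diarrhea is outside the four organ-function groups that 5.2.2 names.

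**Precedence.** Sections 5.1.1 and 6 refer the reader to Section 6 for modifications and delays. Section 6.1 yields expressly to the toxicity-specific rules that follow it. Section 5.2.2 has no such clause.

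**Link to DLTs.** Under 5.4.1 an attributable non-hematologic toxicity that delays the next cycle by more than 14 days is a DLT. Attributable grade 3-4 hyperglycemia is already one by grade, so the delay rule can add a DLT only for lower-grade events.

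**The case against.** The strongest reply is that Section 6 is an operative instruction on delays as well as doses, that 6.4.2 is the specific rule for this toxicity, and that a specific rule naturally prevails over a general cycle-start check. A sensible site may well read it so. But 5.2.2 is worded as mandatory and lists its exceptions. The neutrophil and platelet values it excepts (750 and 75,000; 500 and 50,000 with marrow disease) match Tables 8 and 9, while the metabolic limit was not aligned with 6.4.2. That pattern suggests an omission. The specific-over-general reading has to be supplied by the reader.

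It can also be said that *lower* may be deliberate. Section 3.1.6 limits only acute toxicity of prior therapy to grade 1, so a chronic or disease-related grade 3 event at baseline is possible, and a grade 2 ceiling would then have a function. This stands: that *lower* is a slip for *higher* is an inference. The effect on a patient with baseline grade 0 is the same either way.

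The objection on size stands in full. Insulin or an oral agent starts only at grade 3, at grade 4, or with urine glucose above 0.1 g/dL, and the documents give no rate for that with this combination. Divergent conduct between sites is a risk, not something shown.

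**Conclusion.** Section 5.2.2 is wrong as written in two places, in both lists. The glucose conflict is certain for anyone on insulin or an oral agent whom 6.4.2 would dose. For untreated patients it needs fasting glucose above 160 mg/dL with hyperglycemia still at grade 1-2. The cap bars a patient with baseline grade 0 and a new grade 1 event outside the organ-function list. Both conclusions rest on the literal text and on the absence of a precedence clause.

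The number of affected patients cannot be estimated. A reader might multiply the documented hyperglycemia rates by the 27 evaluable patients (27 × 0.05 = 1.4; 27 × 0.20 = 5.4) and call the result an upper bound. The documents do not support that. Section 2.2.1.2 gives under 5% in the phase 1 study and 5% (related) in the phase 2 study, and Section 7.3 gives 10-20%. All are any-grade and from ganitumab alone, and Section 2.2.1.2 reports that hyperglycemia appeared higher with ganitumab plus gemcitabine than with placebo plus gemcitabine. The fatigue rates (9% related; over 20% in Section 7.3) are likewise context, since how many patients would still have it on Day 1 is not given.

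A reader might also infer that the gate inflates the Cycle 1 DLT count and trips the 3-of-12 pause. That is not supported either: severe attributable hyperglycemia counts already, and no frequency is available for the lower-grade delays. Sample size, power and error rates are untouched. The point should be fixed because following 5.2.2 withholds treatment that Section 6 allows, and the remedy is cheap.

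**What to change.** Make both changes in both lists of Section 5.2.2.

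1. Add to the exceptions: *hyperglycemia that meets the Section 6.4.2 conditions to continue or resume ganitumab (after grade 3-4: asymptomatic, glucose consistently <250 mg/dL without glycosuria, resolved within 2 weeks; insulin or oral agent allowed)*. Keep the existing 6.4.2 reduced-dose provision for grade 3 events that take longer than 2 weeks. State that the exception permits starting the cycle with both drugs, because 6.4.2 speaks only of ganitumab and 5.2.2 governs the whole cycle.
2. Replace the last bullet with: *All other adverse events ≤ grade 1 or baseline, whichever is higher*. This matches 6.1. The clinical team may keep grade 2 as the ceiling instead. Say that 6.1 still governs restart after a DLT.

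The cost is a wording amendment, with no added procedures or patients. The downside is that some patients would start a cycle with stable low-grade events or drug-treated glucose, and an event that was grade 3 at baseline could persist at that grade.
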